### ***3.1.4 Safety Review and Planned Interim Analysis***

To ensure subject safety, safety data will be reviewed on an ongoing basis by the Ionis Safety Physician. Safety data will also be reviewed on an ongoing basis by the Data and Safety Monitoring Board (DSMB). After the last patient within Cohort 1 completes the Day 29 visit, safety results for the cohort will be reviewed by the Medical Monitor and the DSMB and a recommendation regarding further enrollment and escalation to Cohort 2 will be made. The Sponsor and DSMB will determine if enrollment of additional patients is required to confirm there is an acceptable toxicity profile prior to its designation as MTD.

Interim efficacy and safety analyses will be performed to provide content for regulatory submissions and to support ISIS 396443 drug development planning and business activities. Specifically, analyses of primary and secondary efficacy endpoints (Sections 3.2 and 3.3), as well as PK (Section 3.5) and safety analyses (Section 3.6), will be conducted at time points that allow for reasonable interpretation of the data, such as all continuing subjects passing a specific age threshold (e.g., 18, 24 or 36 months).

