Subjects who die or withdraw from the study will be counted as non-responders and will be included in the denominator for the calculation of the proportion. As a result, mortality will be accounted for in the motor milestone analysis. For subjects on permanent ventilation, because motor milestone assessment continues, functional scores after permanent ventilation will be used to assess improvement in motor milestones.

The primary analysis will be the proportion of subjects who achieve improvement in motor milestones at their last available visit. It will be tabulated by cohort and overall. The primary analysis will be conducted using the Evaluable Population.

As the sensitivity analyses, the proportion of subjects who achieve improvement in motor milestones at their last available visit will be tabulated

- 1). by cohort and overall using the 2 SMN2 Copy Set
- 2). by cohort and overall using the Safety Population
- 3). by SMA subtype using the Safety Population

In addition, the following analyses will also be conducted to assess effects of treatment with ISIS 396443 on the motor milestone improvement over time:

- The proportion of subjects who achieve improvement in motor milestones will be tabulated by visit.

Subjects who die or withdraw from the study prior to a visit will be counted as non-responders for the visit and all subsequent visits and will be included in the denominator for the calculation of the proportion. As a result, mortality will be accounted for in the motor milestone analysis. For subjects on permanent ventilation, because motor milestone assessment continues, functional scores after permanent ventilation will be used to assess improvement in motor milestones.

If a subject misses a visit and has visit(s) beyond the visit, then the subject will be counted as a non-responder and included in the denominator for the calculation of the proportion for the visit.

Subjects who are ongoing in the study and haven't reached a visit will not be included in the denominator for the calculation of the proportion for the visit and all subsequent visits.

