- The proportion of subjects who achieve full head control (defined as All the Time Upright), independent sitting (defined as either Prop, Stable Sit or Pivot), rolling (Prone to Supine or Supine to Prone), crawling (defined as crawling On outstretched hand, flat on abdomen, or On hands and knees), standing (defined as Stands with support or Stands unaided), or walking (Cruising (holding on) or Walking independently) at their last available visit. Subjects who die or withdraw from the study will be counted as non-responders and will be included in the denominator for the calculation of the proportion. For subjects on permanent ventilation, because motor milestone assessment continues, functional scores after permanent ventilation will be used to assess improvement in motor milestones.
- The proportion of subjects who achieve full head control (defined as All the Time Upright), independent sitting (defined as either Prop, Stable Sit or Pivot), rolling (Prone to Supine or Supine to Prone), crawling (defined as crawling On outstretched hand, flat on abdomen, or On hands and knees), standing (defined as Stands with support or Stands unaided), or walking (Cruising (holding on) or Walking independently) will be tabulated by visit. Subjects who die or withdraw from the study prior to a visit will be counted as non-responders for the visit and all subsequent visits and will be included in the denominator for the calculation of the proportion. For subjects on permanent ventilation, because motor milestone assessment continues, functional scores after permanent ventilation will be used to assess improvement in motor milestones.

If a subject misses a visit and has visit(s) beyond the visit, then the subject will be counted as a non-responder and included in the denominator for the calculation of the proportion for the visit. Subjects who are ongoing in the study and haven't reached a visit will not be included in the denominator for the calculation of the proportion for the visit and all subsequent visits.

- Summary of change from baseline in the motor milestone total score at their last available visit. The total motor milestone score equals to the sum of individual scores. For example, if the subject cannot maintain head control this is scored as 0, head wobbles as 1, and all the time upright as 2. Complete inability to perform any motor task will therefore be as zero. The ability to master all motor milestones will be scored as 26.

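### At an interim cut, the by-visit responder rates count deaths and withdrawals at visits not yet due but leave out survivors who have not reached them, so late-visit rates can read too low

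*SAP*

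**What the plan says.** SAP 3.2 tabulates the proportion with motor milestone improvement by visit, to show the effect of treatment over time. Two rules set the denominator:

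- Losses: "Subjects who die or withdraw from the study prior to a visit will be counted as non-responders for the visit and all subsequent visits". They stay in the denominator. Nothing limits this to visits that would have fallen due by the data cut.
- Survivors: "Subjects who are ongoing in the study and haven't reached a visit will not be included in the denominator" for that visit or any later one.

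The same pair of rules governs the individual milestones by visit (SAP 3.2), CHOP INTEND response by visit (SAP 3.3.2) and peroneal CMAP response by visit (SAP 3.3.3). All are tabulated by cohort and overall, and by SMA subtype.

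SAP 3.1.4 states: "Interim efficacy and safety analyses will be performed to provide content for regulatory submissions". It names the analyses of Sections 3.2 and 3.3 as in scope and gives as an example of timing "such as all continuing subjects passing a specific age threshold", with 18, 24 or 36 months as possible thresholds. Neither document ends the by-visit tables at visits that all continuing infants have reached.

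**The concern.** Take two infants first dosed on the same date, whose Day 757 falls after the cut. One died on Day 150 and the other is alive and on study. The first is a Day 757 non-responder; the second is not counted at Day 757. Late-visit cells thus hold every loss so far but only those survivors who entered early enough.

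A reader of an interim table could then see response fall at late visits although no survivor has lost function. Entry is staggered: Cohort 2 opens only after the review that follows the last Cohort 1 infant's Day 29 visit (SAP 3.1.4, Protocol 3.6). The distortion can therefore differ between the cohort columns. At stake is a misleading time course in tables meant for regulatory submissions.

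**Working it through.** **The plan's own figures.** The plan gives no expected by-visit rate. Its only efficacy figures are the powers in SAP 3.1.3, Table 1 (n = 20, exact two-sided test, null 5%). The test rejects at 4 or more responders (upper tail 0.0159; at 3 or more it is 0.0755, above 0.025). Power is 58.9%, 77.5%, 89.3% and 95.6% for true rates of 20%, 25%, 30% and 35%, against 58%, 77%, 89% and 95% stated. These agree, and the present point does not affect them.

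**Direction.** At a given visit let R be the survivors who have reached it, π their response rate, D all earlier deaths and withdrawals, and E those among D whose scheduled visit date is on or before the cut (E ≤ D).

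- SAP rate = Rπ / (R + D)
- Date-aligned rate = Rπ / (R + E)

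Because E ≤ D, the SAP rate can never exceed the date-aligned rate. They are equal when every loss was already due for the visit.

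**Where it starts.** Age at screening is at most 210 days (Protocol 5.1) and first dose follows within 21 days (Protocol 3.4.1), so age at first dose is at most 210 + 21 = 231 days. Study day at an age threshold is months × 30.4375 − 231 + 1, compared with the visit days in Protocol Appendix A:

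| Age cut | Lowest study day of a continuing infant | Last visit all have reached | Next visit |
|---|---|---|---|
| 18 months | 318 | Day 253 | Day 337 |
| 24 months | 500 | Day 442 | Day 505 |
| 36 months | 866 | Day 820 | Day 883 |

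This assumes no dosing delays. Up to those visits no survivor is excluded, so the rate is that of the whole analysis set. Later visits, which run to Day 1352, are exposed.

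**Size by arithmetic.** The documents give no loss, accrual or response figures for planning, so these inputs are assumptions. With N = 20, D = 4 and π = 80%, constant over time:

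| Survivors who reached the visit | SAP rate |
|---|---|
| 16 (all) | 12.8/20 = 64.0% |
| 12 | 9.6/16 = 60.0% |
| 8 | 6.4/12 = 53.3% |
| 4 | 3.2/8 = 40.0% |

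Range when a quarter of survivors have reached the visit: with D = 2 the rate falls from 72.0% to 55.4%; with D = 6, from 56.0% to 29.5%; with D = 4 and π = 60%, from 48.0% to 30.0%.

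In whole infants, with 4 losses and 12 responders among 16 survivors, the full rate is 12/20 = 60%. With 8 survivors reached (6 responders) the SAP gives 6/12 = 50%; with 4 reached (3 responders), 3/8 = 38%. If losses are spread over entry dates as survivors are, the aligned rates are 6/(8 + 2) = 60% and 3/(4 + 1) = 60%.

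**Size with staggered entry.** Simulation of 20 infants, uniform entry over 365 days, 20% lost in year 1, 80% response in survivors, and a calendar cut 730 days after first entry:

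| Visit | Mean survivors who reached it | SAP rate | Date-aligned rate |
|---|---|---|---|
| Day 379 | 15.4 | 63.6% | 64% |
| Day 505 | 9.9 | 57.0% | 64% |
| Day 568 | 7.1 | 51.3% | 64% |
| Day 631 | 4.4 | 41.8% | 64% |
| Day 694 | 1.6 | 22.8% | 64% |

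Once all continuing infants have reached Day 1352, both rules give 64.0%.

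A second simulation used the SAP's kind of trigger: all continuing infants past 24 months, uniform entry over 15 months, 25% dying between Days 93 and 400, 75% response in survivors. The two rules differ by about 0 points through Day 568 and about 1 point at Day 631. The SAP rule then gives about 53% at Day 694, 45% at Day 820 and 39% at Day 883, against 56 to 58% when date-aligned. With 10% deaths the Day 883 figures are 58% and 68%. With 25% deaths and a 36-month cut the gap is under 2 points through Day 1009 and about 4 points at Day 1072.

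**The case against.** The strongest reply is that the reach is narrow. The primary analysis uses the last available visit and is untouched. The affected tables are supportive and descriptive, SAP 3.1.1 says the analyses are not comparative, and SAP 3.1.4 attaches no efficacy decision to an interim. The age trigger protects a substantial run of early visits. Any error understates response. The largest falls come from nearly empty cells: in the 24-month scenario Day 946 holds fewer than four survivors on average, and even the date-aligned rate there has a standard deviation of about 25 points across simulated trials.

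All of this stands as a limit on the point. It does not remove it, because an apparent decline produced by the counting rule is still wrong, even when it is conservative. Counting deaths and withdrawals as failures is not in dispute; only visits not yet due are.

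A reader might infer that the plan has no sound view of durability at an interim. The documents do not support that. Milestone total score, CHOP INTEND and CMAP changes are summarised by visit without these denominator rules (SAP 3.2, 3.3.2, 3.3.3), and event-free survival is estimated by Kaplan-Meier at ages from 3 to 30 months (SAP 3.3.1). The affected tables are the only responder view by visit, not the only view over time.

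**Conclusion.** The point holds for the by-visit responder proportions at an interim cut and for nothing else. There, the SAP followed as written can give a late-visit rate that is too low and differs by cohort for reasons of entry date alone. The primary analysis, the change-from-baseline summaries, the Kaplan-Meier analysis and a final analysis with complete follow-up are unaffected.

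The direction follows from the algebra. The size does not: 64% falling to 40% rests on 4 losses in 20, 80% constant response in survivors, and only a quarter of survivors having reached the visit. The start of exposure (after about Day 253, 442 or 820) rests on first dose at up to 231 days of age and no dosing delays.

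A reader might go further and infer that interim rates will fall, or that Cohort 2 will look worse. Neither follows. If every loss was already due for the visit there is no bias, and rising response in survivors can hide it. The cohort effect depends on which infants are lost and when. The change is worth making before an interim table is produced, but it does not threaten the trial's main result.

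**What to change.** In SAP 3.2, 3.3.2 and 3.3.3, count an infant who died or withdrew at a visit only if first-dose date plus the scheduled visit day is on or before the data cut. Apply the same date rule to ongoing infants, with one exception. Protocol 8.7 allows maintenance dosing visits to be delayed by up to 8 weeks, while the window in Appendix A is 7 days. An ongoing infant whose visit is still pending under a permitted delay should stay out of the denominator and not become a non-responder.

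A simpler alternative is to end the interim by-visit responder tables at the last visit all continuing infants have reached. With either option, show the number eligible at each visit.

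The cost is a short change to SAP wording and a date check in the table programs. No new data are needed and a final analysis with complete follow-up does not change. The downside is slightly smaller, or fewer, late-visit cells at interims.

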### **5. SUBJECT ELIGIBILITY**

#### **5.1 Inclusion Criteria**

To be eligible to participate in this study candidates must meet the following eligibility criteria at screening.

1. Signed informed consent of parent(s) or guardian(s)
2. Genetic documentation of 5q SMA homozygous gene deletion or mutation
3. Onset of clinical signs and symptoms consistent with SMA at  $\geq 21$  days and  $\leq 6$  months (180 days) of age
4. Males and females between  $\geq 21$  days and  $\leq 7$  months (210 days) of age at Screening
5. At study entry, receiving adequate nutrition and hydration (with or without gastrostomy), in the opinion of the Site Investigator
6. Body weight  $> 5^{\text{th}}$  percentile for age using CDC guidelines
7. Medical care meets and is expected to continue to meet guidelines set out in the Consensus Statement for Standard of Care in SMA (Wang et al. 2007), in the opinion of the Site Investigator
8. Gestational age of 35 to 42 weeks and gestation body weight  $\geq 2$  kg
9. Reside within approximately 9 hours ground-travel distance from a participating study center for the duration of the study. Residence  $> 2$  hours ground-travel distance from a study center must obtain clearance from the Site Investigator and the study Medical Monitor
10. Able to complete all study procedures, measurements and visits and parent or guardian/subject has adequately supportive psychosocial circumstances, in the opinion of the Site Investigator

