## **1.3 Endpoints**

### ***1.3.1 Primary Endpoint***

The primary endpoint is the proportion of subjects who achieve improvement in motor milestones as evaluated by Module 2 of the Hammersmith Infant Neurological Examination. Improvement is defined as achievement of at least one of the following:

- (i) at least a 2-point increase from baseline or achievement of pincer grasp in the category of voluntary grasp, or
- (ii) at least a 2-point increase in the ability to kick or achievement of touching toes, or
- (iii) a 1-point increase in any of the remaining 6 categories: head control, rolling, sitting, crawling, standing, or walking.

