## 3.2 Primary Efficacy Analysis

Motor milestones will be assessed using Section 2 of the Hammersmith Infant Neurological Exam (HINE) which is comprised of eight independent milestone categories: voluntary grasp, ability to kick in supine position, head control, rolling, sitting, crawling, standing, and walking. Within each of these categories, subjects can progress from complete inability to perform a motor task, for example no grasp, no kicking, unable to maintain head upright, all the way to complete mastery of each category, for example achievement of pincer grasp, touching toes while supine, maintaining their head upright for a maximum of 26 motor milestones (see Table 2 below).

Table 2. Motor Milestone Achievement (Module 2, HINE)

Motor milestone	Milestone progression				
	No grasp	Uses whole hand	Finger and thumb; immature grasp	Pincer grasp	→
Voluntary grasp					
Ability to kick (in supine)	No kicking	Kicks horizontal; legs do not lift	Upward (vertically)	Touches leg	Touches toes
Head control	Unable to maintain upright	Wobbles	All the time upright		
Rolling	No rolling	Rolling to side	Prone to supine	Supine to prone	
Sitting	Cannot sit	Sit with support at hips	Props	Stable sit	Pivots (rotates)
Crawling	Does not lift head	On elbow	On outstretched hand	Crawling flat on abdomen	On hands and knees
Standing	Does not support weight	Supports weight	Stands support	with	Stands unaided
Walking	No walking	Bouncing	Cruising (holding on)	Walking independently	

For each dosing visit, in addition to the scheduled pre-dose assessment, the HINE including motor milestones are also assessed at 3, 6 hours and 1 day after dosing to monitor patient safety. Since the patient's motor function could be temporarily impacted by the lumbar puncture procedure, only the motor milestone results from the pre-dose assessment will be

used for the efficacy analysis and the results at 3, 6 hours and 1 day after dosing will be excluded.

The improvement in motor milestones is defined as achievement of any of the following :

- (i) at least a 2-point increase from baseline or achievement of pincer grasp in the category of voluntary grasp, or
- (ii) at least a 2-point increase in the ability to kick or achievement of touching toes, or
- (iii) a 1-point increase in any of the remaining 6 categories: head control, rolling, sitting, crawling, standing, or walking.

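### The SAP 3.2 milestone tables count a skill held at the visit as achieved, without asking whether the infant already had it at baseline

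*SAP*

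**What the plan says.** After the primary and sensitivity analyses, SAP 3.2 adds further analyses "to assess effects of treatment with ISIS 396443 on the motor milestone improvement over time". Two of them are tables of named skills, one at the last available visit and one by visit. The rows are defined by HINE level: "The proportion of subjects who achieve full head control (defined as All the Time Upright", "rolling (Prone to Supine or Supine to Prone", and so on to "walking (Cruising (holding on) or Walking independently) at their last available visit". Neither table requires a lower level at baseline.

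The denominator rule deals with death and withdrawal: "Subjects who die or withdraw from the study will be counted as non-responders and will be included in the denominator". It does not deal with infants who already had the skill. The SAP promises no baseline column, and the baseline characteristics named in SAP 3.1.1 (an open-ended list) do not include HINE milestones.

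Baseline is defined in SAP 3.1.1 as the last value before the first dose. HINE is scheduled at screening and before dosing on Day 1 (Protocol 6.2.3 and Appendix A), so the data exist.

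On entry, Protocol 5.1 requires "Onset of clinical signs and symptoms consistent with SMA at" 21 to 180 days of age, and an age of 21 to 210 days at screening. Neither 5.1 nor 5.2 has a motor criterion.

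The primary endpoint (SAP 1.3.1, repeated in 3.2) needs a 1-point increase for the same six skills. For the other two categories it reads "at least a 2-point increase from baseline or achievement of pincer grasp in the category of voluntary grasp" and "at least a 2-point increase in the ability to kick or achievement of touching toes".

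**The concern.** The label and the rule do not match. The tables are presented as evidence on improvement and use the word 'achieve', but the rule records status. A programmer following the text would count a skill kept from baseline as achieved on treatment.

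This also departs from the SAP's practice elsewhere. The CHOP INTEND response (3.3.2) is a gain of at least four points from baseline. The CMAP response (3.3.3) is a change from baseline above 0.5 mV. The third clause of the primary rule is an increase.

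There is no control arm, so a reader of a skill row has nothing in the row with which to separate kept skills from gained ones. SAP 3.1.4 also sends the Section 3.2 analyses into interim reports intended for regulatory submissions, where skill-by-skill percentages are easily quoted alone.

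**Working it through.** **The plan's own figure.** The only related figure is the Table 1 power (SAP 3.1.3), which concerns the primary endpoint. With n = 20 and a null rate of 5%, the exact binomial tails are P(X ≥ 3) = 0.0755 and P(X ≥ 4) = 0.0159, so the two-sided 0.05 test rejects at 4 or more responders. Power at 20, 25, 30 and 35% is 58.9, 77.5, 89.3 and 95.6%, against 58, 77, 89 and 95% stated. The table reproduces and does not depend on the skill tables.

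**Inputs.** The sample size of 20 is from SAP Table 1. Cohort sizes of 4, and of 4 to about 16, are from Protocol 10.2. For one skill, let:
- h = infants who have it at baseline;
- b = those among h who still have it at the counted visit;
- k = infants who gain it after the first dose;
- n = the denominator.

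The documents give none of h, b or k, so the values below are assumptions.

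**Formulas.**
- As planned: (b + k)/n
- Newly achieved, all infants: k/n
- Newly achieved, infants without the skill at baseline: k/(n − h)

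The excess of the planned figure over k/n is b/n. Per retained infant this is 1/20 = 5 points overall, 1/16 = 6.25 points in a full Cohort 2, and 1/4 = 25 points in Cohort 1. An infant who had the skill and lost it, died or withdrew adds nothing to the numerator.

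**Illustration** (n = 20, k = 4, all baseline holders keep the skill so h = b):

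| b | Planned (b + 4)/20 | New, all infants 4/20 | New, at risk 4/(20 − b) |
|---|---|---|---|
| 0 | 20% | 20% | 20.0% |
| 1 | 25% | 20% | 21.1% |
| 2 | 30% | 20% | 22.2% |
| 3 | 35% | 20% | 23.5% |
| 4 | 40% | 20% | 25.0% |
| 5 | 45% | 20% | 26.7% |

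With k = 0 and b = 0 to 5, the planned row reads 0 to 25% while nothing has been gained. With b = 0 the rules agree.

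**Which rows are exposed.** Protocol 2.1 says Type I children never sit or walk, so b is probably 0 for sitting and walking. Nothing in the documents rules out full head control or rolling at entry.

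**Would a baseline count alone be enough?** It would give h, and the visit row gives b + k. Their difference is (b + k) − h = k − (h − b), which is gains minus losses. Gains alone need the cross-classification of baseline by visit.

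**Top-level clauses of the primary rule.** SAP Table 2 has four grasp levels (0 to 3) and five kicking levels (0 to 4). An infant at grasp 2 or kicking 3 can gain only one point, so the 2-point rule cannot be met. The alternatives for reaching the top level evidently cover that case. Read literally, they also admit an infant at the top level at baseline and unchanged, a gain of 0 points.

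**The case against.** The strongest reply is that these tables carry little weight and that the same section already measures gain. They are extra descriptive displays, and no test, power figure or decision rests on them. For the same six skills the primary rule demands a 1-point increase. That proportion is also shown by visit, and the total score is summarised as change from baseline; all are repeated by SMA subtype. Status at a late visit is also informative in its own right in a disease where motor neurons degenerate, whether the skill was gained or kept. A by-visit layout could hold a baseline column, and 'achieve' can be read as newly gain.

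Most of this stands, and it limits the point. A reader might infer that retained skills cannot be told apart from gained ones anywhere in the plan; the baseline-referenced analyses show otherwise. What is missing is the split skill by skill. The reply does not remove that gap: no rule says 'achieve' means newly gain, the definitions give only a level, and the SAP does not promise a baseline column.

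A reader might also infer that the primary endpoint is inflated through the pincer-grasp and touching-toes clauses. The documents do not support that. Both clauses sit inside a definition of improvement and have an evident purpose at the ceiling. An infant unchanged at the top level would alter the primary count only by failing every other clause as well.

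Finally, a reader might expect the overstatement to be largest in later-onset infants and so to distort the subtype tables. That is a reasonable guess, but the documents give no baseline milestone data by subtype.

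**Conclusion.** The point holds for the two skill tables in SAP 3.2. As written, they count a skill present before the first dose and still present at the visit as achieved, under a heading about treatment effects on improvement. The excess is b/n, or 5 points per retained infant at n = 20 and 25 points in Cohort 1. It rests on an unknown b: 0 to 5 of 20 infants would give 0 to 25 points, and zero is possible. Head control and rolling are the plausible rows.

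It would go too far to say that pre-dose abilities will in fact be reported as achieved, since that depends on baseline levels the documents do not give. The increase clause of the primary endpoint, the total-score change and the Table 1 power are untouched. The top-level clauses are a matter of wording. This is a worthwhile correction to secondary displays and does not threaten the main efficacy analysis.

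**What to change.** In SAP 3.2, for each skill in both tables:
- show the number who hold it at baseline;
- report newly achieved, meaning at the level at the visit and below it at baseline, with the denominator stated (all infants, or those below the level at baseline) and deaths and withdrawals kept in it as non-responders;
- show infants who held the skill at baseline separately, as maintained or lost;
- label the existing rows as having the milestone at the visit.

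As a wording safeguard only, add to the pincer-grasp and touching-toes clauses in SAP 1.3.1 and 3.2 that the level is reached from a lower baseline level.

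The data are already collected, so the cost is SAP text and an extra column or row or so per table. The downside is that some attainment figures may look less favourable.
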